5.6.1.2. Other Concomitant Medications

The following concomitant medications should be maintained, as much as possible, at stable prescription for at least 28 days prior to Day 1 and throughout the duration of the study.

- Cevilimine or pilocarpine, as prescribed by investigator
- Azathioprine up to a maximum of 2 mg/kg bodyweight/day or 300 mg/day, whichever is lower
- Vitamins, minerals, and herbal supplements
- Hormonal contraceptives or female hormone replacement therapy

• Other chronic therapies including, but not limited to, antihypertensives, thyroid replacement, analgesics, daily aspirin for cardiovascular prophylaxis (≤ 325 mg/day), and chronic nonsteroidal anti-inflammatory drugs (NSAIDs) or other analgesics

5.6.2. Prohibited Concomitant Medications

The prohibited medications are as follows:

Table 2. Prohibited Medications

Drug Class	Agents Disallowed	Prohibited Period	
Biologic Immunomodulator	Anti-tumor necrosis factor drugs infliximab, adalimumab, belimumab, golimumab, certolizumab, rituximab (CD19+ B cells must be present), dupilumab, or biosimilar agent (if applicable)	90 days prior to screening through the end of study participation	
	Any other investigational immunomodulatory biologic agent or biosimilar (if applicable)	90 days or 5 half-lives prior to screening (whichever is longer) through the end of study participation	
Prohibited CLE Medica	ntions		
Corticosteroids	Oral corticosteroids > 10 mg prednisone equivalent/day	28 days prior to Day 1 through the end of study participation	
	Injectable corticosteroids	28 days prior to Day 1 through the end of study participation	
	Class I-IV topical corticosteroids	28 days prior to Day 1 through the end of study participation	
Non-biologic Immunomodulator	Azathioprine (> 2 mg/kg bodyweight/day or 300 mg/day, whichever is lower), colchicine, cyclosporine, dapsone (>100 mg/day), tacrolimus (oral or topical), gold salts, minocycline, MTX > 20 mg/week (subcutaneous or oral), mycophenolate, penicillamine, sirolimus or other immunomodulatory/immunosuppressive therapies (with the exception of oral antimalarials as permitted in Section 5.6.1.1)	28 days prior to Day 1 through the end of study participation	
Strong P-gp Inducers ^a			
Anticonvulsants	Phenobarbital, phenytoin, or carbamazepine	21 days prior to Day 1 through the end of study participation	
Antimycobacterials	Rifabutin, rifapentine, rifampin		
Herbal/Natural Supplements	St. John's wort or danshen (salvia miltiorrhiza)		

Drug Class	Agents Disallowed	Prohibited Period			
CYP3A4 Inhibitors ^b					
Strong CYP3A4 Inhibitors	Clarithromycin, conivaptan, itraconazole, ketoconazole, nefazodone, posaconazole, telithromycin, voriconazole, telaprevir, boceprevir, grapefruit juice, idelalisib, Viekira Pak (ombitasvir, paritaprevir, ritonavir, dasabuvir), troleandomycin, or mibefradil	14 days prior to Day 1 through the end of study participation			
Moderate CYP3A4 Inhibitors	Fluconazole, erythromycin, diltiazem, dronedarone, aprepitant, casopitant, imatinib, verapamil, tofisopam, ciprofloxacin, cimetidine, cyclosporine, Schisandra sphenanthera, crizotinib, netupitant, nilotinib, or isavuconazole	14 days prior to Day 1 through the end of study participation			
CYP3A4 Inducers ^c					
Strong CYP3A4 Inducers	Carbamazepine, phenytoin, rifampin, fosphenytoin, pentobarbital, primidone, rifabutin, rifapentine, phenobarbital, mitotane, avasimibe, St. John's Wort, enzalutamide	14 days prior to Day 1 through the end of study participation			
Moderate CYP3A4 Inducers	Bosentan, thioridazine, nafcillin, modafinil, semagacestat, genistein	14 days prior to Day 1 through the end of study participation			
Other					
JAK Inhibitor	Ruxolitinib or tofacitinib (or investigational)	3 months prior to screening through the end of study participation			
SYK Inhibitor	Fostamatinib or entospletinib (or investigational)	3 months prior to screening through the end of study participation			
Anti-platelet	Adenosine diphosphate (ADP) receptor inhibitors, phosphodiesterase inhibitors, PAR-1 antagonists, glycoprotein 2b/3a inhibitors	One year prior to screening through the end of study participation			
	Aspirin > 325 mg/day	14 days prior to Day 1 through the end of study participation			
Anti-coagulant	Warfarin, any Vitamin K antagonist, any novel oral anticoagulant, any heparin or low molecular heparins, or inhibitors of factor Xa	One year prior to screening through the end of study participation			

May result in a decrease in the concentrations of filgotinib. Filgotinib is a P-gp substrate. A single dose of 200 mg itraconazole (a potent P-gp inhibitor) increased filgotinib C_{max} by 63.9% and AUC_{inf} by 44.6% but had no effect on the major, active metabolite GS-829845.

b May result in an increase in the concentrations of GS-9876

c May result in a decrease in the concentrations of GS-9876

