4.2. Inclusion Criteria

Subjects must meet *all* of the following inclusion criteria to be eligible for participation in this study.

- 1) Female, ≥ 18 to ≤ 75 years of age at the time of initial written informed consent
- 2) Must have a diagnosis of CLE (CCLE (eg, DLE) or SCLE), per investigator evaluation, with the following:
 - a) Moderately-to-severely active CLE {Klein 2010}, with a CLASI activity score ≥ 10 at screening and Day 1
 - b) Prior intolerance or inadequate response (per investigator judgment) to at least one of the following medications *for the treatment of CLE*:
 - Topical corticosteroids or topical tacromilus, administered for ≥ 3 months
 - Oral corticosteroids ≥ 10 mg/day taken for ≥ 3 months
 - A conventional synthetic disease-modifying antirheumatic drug (csDMARD), including, but not limited to: chloroquine, quinicrine, hydroxychloroquine, azathioprine, mycophenolate, leflunomide, dapsone, or MTX, administered for ≥ 3 months
 - A bDMARD (such as belimumab or abatacept) administered for ≥ 3 months, or ≥ 1 dose of a cell-depleting bDMARD, such as rituximab. Subjects with prior exposure to a B-cell depleting bDMARD (at any time) must have presence of CD19+ B cells by flow cytometry at screening
- 3) Subjects using antimalarials and/or topical and/or oral corticosteroids (≤ 10 mg prednisone) must agree to one of the follow (a or b):
 - a) Continue stable doses from 28 days prior to Day 1 through Week 12 of the study (see Section 5.6.1 for dose restrictions and other details)
 - b) Discontinue these medications at least 28 days prior to Day 1
- 4) Females of childbearing potential (as defined in Appendix 5) must have a negative pregnancy test at screening and Day 1

- 5) Subjects of childbearing potential (as defined in Appendix 5) who engage in heterosexual intercourse must agree to use protocol specified method(s) of contraception as described in Appendix 5
- 6) Lactating subjects must agree to discontinue nursing starting from the time of written consent through the study and for 36 days after their last dose of study drug
- 7) Subjects must agree not to undergo in vitro fertilization or donate their eggs for reproductive purposes, starting at the time of written consent through the study and for 36 days after their last dose of study drug
- 8) Meet either of the following tuberculosis (TB) screening criteria (a or b):
 - a) No evidence of active or latent TB:
 - Negative history of TB infection and

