4.3. Exclusion Criteria

Subjects who meet *any* of the following exclusion criteria are not to be enrolled in this study.

- 1) Have active SLE or Sjogren's syndrome (SjS) that requires use of a prohibited medication (refer to Section 5.6.2). Systemic lupus erythematosus or SjS that is readily managed with protocol-permitted medications is allowed, per investigator judgment
- 2) Have another highly active inflammatory/autoimmune/rheumatic disease (such as highly active RA, nephritis, or CNS inflammation) which would compromise subject safety or interfere with the conduct of the study (per investigator judgment). Stable conditions, eg, stable thyroiditis, are permitted
- 3) Previous dosing within 3 months of screening with a JAK inhibitor or SYK inhibitor (marketed or investigational)
- 4) Previous history of cyclophosphamide use (at any time)
- 5) Known hypersensitivity to the study drugs, their metabolites, or formulation excipients
- 6) Major surgery (requiring regional block or general anesthesia) within 30 days prior to screening, or planned during the study
- 7) Active infection that is clinically significant, per investigator judgment, or any infection requiring hospitalization or treatment with intravenous anti-infectives within 60 days prior to screening; or any infection requiring oral anti-infective therapy within 30 days prior to screening
- 8) Subjects who are pregnant, breastfeeding, or planning to become pregnant or breastfeed during the study or for 36 days after their last dose of study drug
- 9) A positive test result for human immunodeficiency virus (HIV)-1 and 2 antibody at or prior to screening
- 10) Positive for HCV antibodies at screening. Subjects with positive HCV antibody (Ab) will require reflex testing for HCV RNA. Subjects with positive HCV RNA viral load (VL) at screening will be excluded. Subjects with positive HCV Ab, but negative HCV RNA VL are eligible per investigator judgment, but require ongoing monitoring as outlined in the schedule of assessments
- 11) Positive for hepatitis B surface antigen (HBsAg) or HBV core antibodies at screening (regardless of HBV VL)
- 12) History of malignancy within the last 5 years prior to screening (except for successfully treated basal cell carcinoma or non-metastatic squamous cell carcinoma of the skin or cervical carcinoma in situ, with no evidence of recurrence)

- 13) History of lymphoproliferative disorder or current lymphoproliferative disease

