- 14) History of organ or bone marrow transplant
- 15) Use of prohibited concomitant medications per Section 5.6.2
- 16) Any chronic, uncontrolled medical condition which would put the subject at increased risk during study participation, such as uncontrolled: diabetes, hypertension, morbid obesity, thyroid, adrenal, pulmonary, hepatic, renal, neurologic or psychiatric disease, or other disease of concern, as per judgment of investigator
- 17) Administration of a live/attenuated vaccine within 4 weeks prior to Day 1, or planned during the study or for 12 weeks after subject's last dose of study drug
- 18) History of opportunistic infection or immunodeficiency syndrome, which would put the subject at risk, per investigator judgment
- 19) Currently on systemic (oral or intravenous) anti-infective therapy for chronic infection (such as pneumocystis [PCP], cytomegalovirus [CMV], Herpes zoster, and atypical mycobacteria). Past history of disseminated Staphyloccoccus aureus or disseminated Herpes simplex infection
- 20) History of symptomatic Herpes zoster or herpes simplex within 12 weeks of screening, or any history of disseminated Herpes simplex, Herpes zoster, ophthalmic zoster, or central nervous system zoster
- 21) Blood loss, donation (> 500 mL), or blood product transfusion within 12 weeks of Day 1
- 22) Known bleeding disorder or hypercoagulable state; antiphospholipid antibody (APLA) syndrome with prior clinically significant event (per judgment of investigator); or on chronic anticoagulation/anti-platelet therapy such as warfarin, heparin, etc, as outlined in Section 5.6.2 (NOTE: stably prescribed chronic aspirin therapy ≤ 325 mg/day for cardiovascular prophylaxis is allowed)
- 23) Current drug or alcohol abuse, per judgment of investigator
- 24) Any condition or circumstances which in the opinion of the investigator may make a subject unlikely or unable to complete the study or comply with study procedures and requirements
- 25) Participation in any clinical study of an investigational drug within 4 weeks or 5 half-lives prior to screening, whichever is longer. Exposure to investigational biologics should be discussed with the Gilead medical monitor

- 26) Tests performed at the central laboratory at screening that meet any of the criteria below (at the investigator's discretion, out of range lab values may be retested one time to rule out laboratory error):
 - i) Hemoglobin < 8.0 g/dL (International System of Units [SI]: < 80 g/L);

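### Inclusion 2b accepts abatacept as a qualifying prior biologic, but Table 2 leaves it out of the 90-day biologic washout, so as little as 28 days before Day 1, or no stated period, may apply.

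*Protocol*

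**What the plan says.** Protocol Section 4.2, inclusion 2b, requires intolerance of, or inadequate response to, at least one earlier CLE treatment. One qualifying option is "A bDMARD (such as belimumab or abatacept) administered for ≥ 3 months". The criterion sets no washout period.

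Washouts are in Protocol Section 5.6.2, Table 2. Three entries matter here:

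- **Biologic Immunomodulator, first row.** It names "infliximab, adalimumab, belimumab, golimumab, certolizumab, rituximab (CD19+ B cells must be present), dupilumab, or biosimilar agent (if applicable") and requires 90 days off before screening. Belimumab is on the list; abatacept is not.
- **Biologic Immunomodulator, second row.** It covers "Any other investigational immunomodulatory biologic agent or biosimilar (if applicable"), with 90 days or 5 half-lives before screening, whichever is longer.
- **Non-biologic Immunomodulator row.** Its list closes with "sirolimus or other immunomodulatory/immunosuppressive therapies (with the exception of oral antimalarials as permitted in Section 5.6.1.1"), and the period is 28 days before Day 1.

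Exclusion 15 in Section 4.3 ("Use of prohibited concomitant medications per Section 5.6.2") enforces the table and adds nothing to it. Exclusion 25 concerns participation in studies of investigational drugs and ends: "Exposure to investigational biologics should be discussed with the Gilead medical monitor". Section 5.6.1.1 lists the concomitant CLE medications that are allowed, and abatacept is not among them.

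**The concern.** The protocol expects some subjects to arrive having taken abatacept, because it offers the drug as an example of a qualifying treatment. Every biologic that Table 2 names must be stopped 90 days before screening. The one other biologic that inclusion 2b names falls outside that rule, and no reason is given.

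The main stake is safety. A subject could start a JAK1 or SYK inhibitor much sooner after abatacept than after belimumab. Protocol Section 1.5 counts serious infection as an important potential risk of filgotinib and describes clinical experience with GS-9876 as limited.

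The second stake is consistency. About 20 centers have to decide whether a biologic belongs in a row headed non-biologic, and they may decide differently.

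**Working it through.** The plan states no figure to reproduce. The check has two steps: find which row of Table 2 can reach abatacept, then put the two washouts on one time scale.

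**Which row applies**

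1. First biologic row: abatacept is not named.
2. Second biologic row: limited to investigational agents. Where the protocol means both kinds it says so, as in exclusion 3: "Previous dosing within 3 months of screening with a JAK inhibitor or SYK inhibitor (marketed or investigational"). I assume that abatacept is a marketed drug, as its use in inclusion 2b implies; the documents do not state its status.
3. Non-biologic row: the closing catch-all is worded broadly enough to include abatacept, but only if the row heading is set aside.
4. Exclusions 15 and 25: the first points back to the table and the second concerns investigational products. Neither supplies a washout.

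**Size of the difference**

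Let S be the number of days from screening to Day 1. Section 6.2.1 allows S from 0 to 28.

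| Quantity | Formula | S = 0 | S = 28 |
|---|---|---|---|
| Belimumab, days off before Day 1 | 90 + S | 90 | 118 |
| Abatacept under the catch-all, days off before Day 1 | 28 | 28 | 28 |
| Abatacept under the catch-all, days off before screening | 28 − S | 28 | 0 |
| Shortfall against belimumab | (90 + S) − 28 = 62 + S | 62 | 90 |

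In practice S = 0 is unlikely, because eligibility needs central laboratory results and subjects return for randomization. The shortfall of 62 days is therefore a floor. On the literal reading of the row heading no period is stated, and the whole 90 to 118 days is missing.

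**What the difference could mean for residual drug**

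The documents give no half-life for abatacept. Assuming simple exponential decline, the fraction left after d days with half-life h is 0.5^(d/h).

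| Assumed h (days) | Left after 28 days | Left after 90 days |
|---|---|---|
| 7 | 6% | 0.01% |
| 10 | 14% | 0.2% |
| 14 | 25% | 1.2% |
| 21 | 40% | 5% |

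The table illustrates exposure only. It does not estimate infection risk.

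**The case against.** **The investigational row may already cover abatacept.** One could say that abatacept is investigational when used off-label in CLE, which would give 90 days or 5 half-lives. Table 2 is also loosely drafted: its JAK and SYK rows name a few drugs and then add investigational ones, which is narrower than exclusion 3. This reading cannot be ruled out, so 28 days is not a firm upper limit on every reading. It is weak, though. Inclusion 2b treats abatacept as ordinary prior therapy alongside belimumab, and belimumab is named in the table rather than left to the investigational row.

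**Inclusion 2b is a history criterion.** It groups drugs that are handled differently elsewhere: hydroxychloroquine may continue and mycophenolate must stop. Being listed together does not by itself require equal washouts. That is correct. The stronger argument is that every biologic named in Table 2 gets 90 days, while 28 days is the period for corticosteroids and non-biologic drugs.

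**Concurrent use is already limited.** A reader might infer that the protocol lets subjects stay on abatacept for CLE. Section 5.6.1.1 does not support that. Exclusion 1 also narrows the field: "Systemic lupus erythematosus or SjS that is readily managed with protocol-permitted medications is allowed, per investigator judgment". What remains is a subject with another stable disease. Exclusion 2 permits stable conditions, SAP Section 5.2 tabulates RA at baseline, and Section 5.6.1.2 allows other chronic therapies through an open-ended list.

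**Harm is not shown.** The protocol accepts background methotrexate, low-dose prednisone and azathioprine. It manages infection through exclusions 7 and 18 to 20, the interruption and discontinuation rules in Section 3.5, and DMC safety review. These points stand: the risk is plausible, but nothing in the documents puts a number on it.

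**Conclusion.** The gap is real and modest. On the most natural protective reading, abatacept and other unlisted marketed biologics need 28 days off before Day 1, which is 62 to 90 days less than belimumab. On a literal reading of the row heading, Table 2 sets no washout. The conclusion rests on abatacept being a marketed drug and on rejecting the off-label-as-investigational reading.

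A reader might go further and infer that carry-over threatens the efficacy result. The documents do not support that. CLASI activity of at least 10 is required at both screening and Day 1, which limits enrolment of subjects whose disease is still suppressed. The treatment-policy estimand in SAP Section 3.9 uses all observed values, so the primary analysis is unchanged. Unclear prohibited status could at most blur an intercurrent event in the supportive hypothetical estimand, and only for use during the study.

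The number of subjects affected, out of about 50 planned, cannot be derived and is likely to be small. The case for change is an inexpensive safeguard and uniform eligibility.

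**What to change.** Amend three entries of Table 2 in Protocol Section 5.6.2:

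1. Add abatacept to the first biologic row, with the same period as belimumab: from 90 days before screening until study participation ends.
2. In the second biologic row, insert *marketed or* before *investigational*, and keep its period.
3. In the non-biologic row, limit the closing catch-all to *other non-biologic* therapies, so that no biologic falls under two rows.

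Exclusion 15 then applies without further edits.

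One side effect is that unlisted marketed biologics would fall under 90 days or 5 half-lives, while named ones keep a flat 90 days. The two differ only when the half-life exceeds 90 / 5 = 18 days, and the difference is then in the cautious direction.

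The cost is a small protocol amendment and an occasional subject with recent biologic use who is deferred or excluded. Sample size and analysis are untouched.

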5.7. Vaccine Guidelines

Prior to study participation, it is recommended that the subject's vaccinations be brought up to date according to local vaccination standards.

Live or attenuated vaccines (including, but not limited to varicella and inhaled flu vaccine) are prohibited within 4 weeks of Day 1, throughout the study, and for 12 weeks after the last dose of study drug.

Subjects should be advised to avoid routine household contact with persons vaccinated with live/attenuated vaccine components. General guidelines suggest that a study subject's exposure to household contacts should be avoided for the below stated time periods:

- Varicella or attenuated typhoid fever vaccination avoid contact for 4 weeks following vaccination
- Oral polio vaccination avoid contact for 6 weeks following vaccination
- Attenuated rotavirus vaccine avoid contact for 10 days following vaccination
- Inhaled flu vaccine avoid contact for 1 week following vaccination

Inactivated vaccines (such as inactivated flu vaccines) should be administered according to local vaccination standards whenever medically appropriate; however, there are no available data on the concurrent use of filgotinib or GS-9876 and their impact on immune responses following vaccination.

5.8. Accountability of Study Drugs

The investigator is responsible for ensuring adequate accountability of all used and unused study drug. This includes acknowledgement of receipt of each shipment of study drug (quantity and condition). All used and unused study drug dispensed to subjects must be returned to the site.

Study drug accountability records will be provided to each study site to:

- Record the date received and quantity of study drug
- Record the date, subject number, subject initials, the study drug number dispensed
- Record the date, quantity of used and unused study returned, along with the initials of the person recording the information.

5.8.1. Study Drug Return or Disposal

For additional information about study drug accountability, return, and disposal, refer to Section 9.1.7.

6. STUDY PROCEDURES

The study procedures to be conducted for each subject enrolled in the study are presented in tabular form in Appendix 2 and described in the text that follows. Additional information is provided in the study procedures manual.

The investigator must document any deviation from protocol procedures and notify the sponsor or contract research organization (CRO).

6.1. Subject Enrollment and Treatment Assignment

Subject eligibility will be established at the conclusion of the screening evaluations. The screening number and subject ID will be assigned for each subject by IWRS.

It is the responsibility of the investigator to ensure that each subject is eligible for the study before randomization. A subject will be considered enrolled once they have been randomized.

6.2. Pretreatment Assessments

6.2.1. Screening Visit

Subjects will be screened up to 28 days prior to randomization (Day 1) to determine eligibility for participation in the study.

The following will be performed and documented at screening:

- Obtain written informed consent.
- Review of inclusion/exclusion criteria
- Obtain medical history (including demographics, surgical history, and CLE history with documentation of prior skin biopsy results, if available)
- Complete PE
- Height
- Weight
- Vital signs (blood pressure, heart rate, respiratory rate, and temperature)
- PGA
- CLASI
- Standard 12-lead ECG
- Obtain blood samples for:
 - Clinical Laboratory Tests (hematology, serum chemistry, and coagulation)

- Endocrine Tests (HbA_{1c} and TSH)
- Erythrocyte sedimentation rate (ESR) and C-reactive protein (CRP)
- Serum Pregnancy Test (for females of childbearing potential) or FSH test (for females of nonchildbearing potential)
- Virology Tests (HIV-1, HIV-2, HBV, and HCV)
- QuantiFERON® TB Gold in Tube Test (if applicable)
- Biomarker Samples
 - Whole Blood, Cytochex
 - o Whole Blood, Heparin
 - o Serum and plasma biomarker samples
 - o vfPBMC sample
 - PAXgene RNA sample
- Obtain urine samples for:
 - Urinalysis
 - Urine Drug and Alcohol test
 - Urine protein to creatinine ratio
- Chest x-ray (if not obtained within 3 months prior to screening, with films or report available for investigator review)

Subjects meeting all of the inclusion criteria and none of the exclusion criteria will return to the clinic for randomization into the study on Day 1.

Subjects who do not meet the eligibility criteria will be excluded from randomization and may be considered for rescreening one time for the study in consultation with the sponsor or its designee. Refer to Section 4.4 for additional details.

From the time of obtaining informed consent through the first administration of investigational medicinal product, record all SAEs, as well as any AEs related to protocol-mandated procedures on the AE eCRF and any concomitant medications in the concomitant medication eCRF. All other untoward medical occurrences observed during the screening period, including exacerbation or changes in medical history are to be captured on the medical history eCRF. See Section 7.6 Adverse Events and Toxicity Management for details.

